1.2.3 Pharmacodynamic Endpoints

Data from COR-001-treated patients from Cohorts not exceeding the MTD will be pooled and data from all placebo patients will be pooled for the pharmacodynamic endpoint analyses. Dose-relationships will be explored by also presenting data by dose regimen (i.e., 2 mg Q2 weeks, 6 mg Q2 weeks, 20 mg Q2 weeks, and pooled placebo).

1.2.3.1 Primary Pharmacodynamic Endpoints

- Change from baseline (mean of Full Screening and Day 1 values) in hsCRP to Week 4 between treatment groups
- Change from baseline (mean of Full Screening and Day 1 values) in SAA to Week 4 between treatment groups

1.2.3.2 Secondary Pharmacodynamic Endpoints

- Change from baseline (mean of Screening and Day 1 values) in TSAT to Week 4
- Change from baseline (mean of Screening and Day 1 values) in the CHr to Week 4
- Change from baseline (mean of Full Screening and Day 1 values) in hsCRP to the mean of Weeks 10-12
- Change from baseline (mean of Full Screening and Day 1 values) in SAA to the mean of Weeks 10-12
- Change from baseline (mean of Full Screening and Day 1 values) in serum pre-albumin to the mean of Weeks 10-12 and albumin to Week 12
- Change from baseline (weekly mean of Screening) in ERI to Week 4
- Change from baseline (weekly mean of Screening) in ERI to the mean of Weeks 8 – 12
- Change from baseline (mean of Full Screening and Day 1 values) in Hemoglobin to Week 4
- Change from baseline (mean of Full Screening and Day 1 values) in Hemoglobin to Week 10-12
- Change from baseline (mean of Full Screening and Day 1 values) in Hemoglobin to Week 10-12, excluding hemoglobin values following a change in the total weekly ESA dose. A change is defined as the first time when the ESA weekly dose goes up by >25% or down by >25% relative to the previous week's dose.
- Change from baseline (weekly mean of Full Screening) in ERI to the mean of Weeks 10 – 12
- Change from baseline (mean of Full Screening and Day 1 values) in TSAT to Week 10-12
-
- Change from baseline (mean of Full Screening and Day 1 values) in the CHr to Week 10-12
-
- Change from baseline (mean of Full Screening and Day 1 values) in serum albumin to Week 12

Exploratory Pharmacodynamic Endpoints

- Description of the systemic iron availability (TSAT, absolute reticulocyte count,

hemoglobin, CHr) over time

- Description of markers of malnutrition-inflammation (pre-albumin and albumin) over time
- Description of systemic iron stores (serum ferritin, hepatic and splenic iron content by MRI, and supplemental iron dose requirements) over time
- Description of ERI change from baseline (weekly mean during the Screening Period) through Week 24
- Description of changes ESA and parenteral iron dose requirements from baseline (weekly mean during the Screening Period) to Evaluation Period (Weeks 8 – 12) and through Week 24
- Description of changes in LV mass index from Screening to Week 12
Description of changes in pre-dialysis, post-dialysis, and delta-serum Troponin and NT-proBNP (defined as the difference between the pre- and post-dialysis troponin) from baseline (mean of Screening) to Weeks 10 – 11
- Description of handgrip strength from baseline (during Screening) to Week 12
- Description of the FACIT fatigue score from baseline (during Screening) to Week 12

Specifically ERI is calculated as follows:

For patient receiving epoetin alfa:

$$\frac{\text{Total weekly dose of epoetin alfa (units)}}{(\text{hemoglobin [g/dL]} * \text{target dry body weight [kg]})}$$

For patients receiving darbepoetin alfa:

$$\frac{\text{Total weekly dose of darbepoetin alfa (mcg)} * 300}{(\text{hemoglobin [g/dL]} * \text{target dry body weight [kg]})}$$

For patients receiving methoxy polyethylene glycol-epoetin beta:

$$\frac{\text{Weekly dose of methoxy polyethylene glycol-epoetin beta (mcg)} * 300}{(\text{hemoglobin [g/dL]} * \text{target dry body weight [kg]})}$$

1.3 SUMMARY OF THE STUDY DESIGN

1.3.1 General Study Design and Plan

[figure not shown]
This is a randomized, double-blind, placebo-controlled trial designed to evaluate the safety, pharmacokinetics, and pharmacodynamic effects of multiple doses of COR-001 or placebo administered to sequential cohorts of hemodialysis patients.

Within each dosing cohort ten hemodialysis patients will be randomized to COR-001 or placebo at ratio of 8 to 2. Prior to dose escalation there will be a formal safety review by the Safety Review Committee (SRC). The SRC will specifically determine whether MTD has been exceeded based on protocol-defined DLT occurring through Study Day 21 in the 8 actively-treated patients in the current cohort (see Figure 1). In addition, pharmacokinetic and pharmacodynamic results will be reviewed to assess the appropriateness of the next planned dose and to guide revision of the next dose to be evaluated, if necessary. The planned doses are shown in Table 1. These doses may be adjusted based on accruing data; however, the maximum dose to be studied will not exceed the planned total dose in Cohort 4 (60 mg every 14 days [6 doses]).

A single interim analysis was planned to enable future program planning.

Patients will undergo an up to 4-week Screening Period. Those who meet the entry criteria will be randomized on Day 1 (a dialysis day) (or Day -1 with approval) and will receive the first dose of study drug during dialysis. Additional visits will follow the schedule of events (Appendix A, Section 15.1 of protocol). All subsequent study drug infusions will also be administered during dialysis and study visits will coincide with regularly scheduled dialysis treatments. Patients dropping out for reasons unrelated to safety may be replaced. Following the 12-week Treatment Period, patients will be followed for an additional 12 weeks for safety. The patients will have completed their primary study participation at Week 24 (end of the Safety Follow-Up Period). Sparse blood samples will be additionally collected on Week 35 for anti-drug antibodies, pharmacokinetics, and IL-6 measurements as part of an Extended Follow-Up Period.

Figure 1 Dose Escalation Schematic

The MTD assessment will be based on safety data from Weeks 1 to 3. If more than 2 of 8 active patients in a cohort experience a DLT, the MTD will be considered to have been exceeded.

¹If the MTD is not exceeded, dose escalation may continue.

²If the MTD is exceeded, a lower dose, including previously studied dose, may be selected.

The planned doses shown here may be adjusted based on accruing data. The highest dose that will be studied is a cumulative dose of 360 mg. Expansion cohorts to further evaluate doses below the dose that exceeded the MTD may be initiated at any time.

Table 1 Planned COR-001 Doses, Serial Dilutions and Administered Volumes

DOSE COHORT	DOSING REGIMEN	DRUG STOCK CONCENTRATION (MG/ML IN STERILE WATER)	# OF SERIAL DILUTIONS (1ML DRUG STOCK ADDED TO 2ML DILUTION VIAL FOR FINAL VOLUME OF 3ML)	DILUTED DRUG VOLUME TO BE USED (ML)	IVBP VOLUME TO BE ADDED TO SALINE INFUSION BAG (IN 100ML SALINE)	TOTAL VOLUME TO BE ADDED TO 100ML 0.9% SALINE
1	2 mg every 14 days	50	3	1.1	1.8	2.9
2	6 mg every 14 days	50	2	1.1	1.8	2.9
3	20 mg every 14 days	50	1	1.2	1.8	3.0
4	60 mg every 14 days	50	0	1.2 (0.6ml from 2 drug vials)	1.8	3.0

1.3.2 Sample Size and Statistical Power Considerations

The primary objective of this study is to determine the maximum tolerated dose. The MTD will be exceeded and stopping criteria for that dose will have been met if more than 2 of 8 COR-001-treated patients in a cohort experience a DLT ($\geq 25\%$). With 8 patients dosed in each cohort and at the expected DLT rate of 25%, the probability of observing 2 or more patients with DLT is greater than 63% and the probability of observing at least 1 patient with DLT is 90%.

Sample size calculations were performed for hsCRP, TSAT, and CHR based on the literature (Coyne 2007 and Sieper 2013). For 80% power to observe an hsCRP difference from placebo of -10.6 mg/dL with a common standard deviation of 17.3 the sample size required is 43 patients in each group. With effect sizes ranging from 0.46 to 0.77, the sample size ranges from 76 to 28 patients. The sample size with 80% power required to observe a TSAT difference of 5.7 with a common standard deviation of 6.4 (effect size of 0.89) is 21 patients, with effect sizes ranging from 1.12 to 0.67 requiring 28 to 76 patients. The sample size with 80% power required to observe a CHR difference of 0.9 pg with a common standard deviation of 1.92 is 73, with effect sizes ranging from 0.59 to 0.35 requiring sample size from 47 to 128 patients. All sample size calculations were done with two sided t-tests and a significance level of $\alpha = 0.05$.

2. STATISTICAL METHODS

2.1 GENERAL CONSIDERATIONS

Unless otherwise specified, all study-collected data will be summarized by treatment group using descriptive statistics, graphs, and/or raw data listings. Descriptive statistics for continuous variables will include number of patients (n), mean, standard deviation (SD), median, quartiles (Q1 and Q3), minimum (min) and maximum (max) values. Analysis of categorical variables will include frequency and percentage.

P-values will be rounded to three decimal places. If a p-value is less than 0.001 it will be reported as “<0.001.” If a p-value is greater than 0.999 it will be reported as “>0.999.” 95% confidence intervals will be estimated for pharmacodynamic endpoints.

For the analyses to be used for SRC, the subjects will be summarized by treatment group within each cohort. The placebo group will not be pooled.

For the final CSR report, the subjects will be summarized according to their treatment group. The placebo subjects at each cohort will be pooled into one group, and the subjects treated with COR-001 will be summarized based on the dosing regimen.

2.2 DEFINITIONS OF ANALYSIS SETS

The number of subjects entered, the number and the percentage of subjects included in each analysis set, and the number and the percentage of subjects excluded from each analysis set will be presented by dose group, treatment and overall.

Intent-to-treat (ITT) analysis population: The ITT analysis population will be defined as all randomized patients. Treatment classification will be based on the randomized treatment. This will be the primary population for the analyses of disposition and baseline data.

Pharmacodynamic analysis population: The pharmacodynamic population will be defined as all ITT patients who were treated with their assigned study drug treatment, had any pharmacodynamic assessments, and did not have certain important protocol deviations described below. This will be the population for the pharmacodynamic analyses.

- ≥ 2 Missed doses or ≥ 2 incorrect doses
- Important protocol deviations that are determined to significantly affect interpretation of PD endpoints, identified prior to unblinding of the study.
 - Minor departures from the ESA dosing guidelines in the protocol will not be considered major deviations.

For subjects who do not receive the assigned dose at any time during treatment, the dose will be defined as the highest dose received.

Pharmacokinetics analysis population: The PK population will be defined as all patients who have any valid samples measured for Study Drug levels. This will be used for PK analysis.

Safety analysis population: The safety analysis population will consist of all patients randomized and treated with any amount of study medication (COR-001 or placebo). Treatment classification will be based on the actual treatment received. This population will be used for the safety analyses.

MTD analysis Population: The MTD analysis population will be a subset of safety analysis population by excluding subjects replaced due to a non-safety reason. This population will be used for MTD and DLT analyses.

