11.3 General Statistical Considerations and Definitions

11.3.1 *General Statistical Methods*

All study-collected data will be summarized by treatment group using descriptive statistics, graphs, and/or raw data listings. Descriptive statistics for continuous variables will include number of patients (n), mean, standard deviation (SD), median, quartiles (Q1 and Q3), minimum (min) and maximum (max) values. Analysis of categorical variables will include frequency and percentage.

11.3.2 *Analysis Populations*

Intent-to-treat (ITT) analysis population: The ITT population will be defined as all randomized patients. Treatment classification will be based on the randomized treatment. This will be the primary population for the analyses of disposition and baseline data.

Pharmacodynamic analysis population: The pharmacodynamic population will be defined as all ITT patients who received their assigned Study Drug, had any pharmacodynamic assessments, and did not have major protocol violations. This will be the population for the pharmacodynamic analyses.

Per-protocol analysis population: The subset of the pharmacodynamics population that did not have a major protocol deviation, as defined in the SAP. The Per-Protocol analysis population will be used to perform the sensitivity analysis for the pharmacodynamics endpoints.

Pharmacokinetics analysis population: The PK population will be defined as all patients who have any valid samples measured for Study Drug levels. This will be used for PK analysis.

MTD analysis Population: The MTD analysis population will be defined as a subset of safety analysis population by excluding subjects replaced due to a non-safety reason. Treatment classification will be based on the actual treatment received. This population will be used for MTD and DLT analyses.

Safety analysis population: The safety population will consist of all patients randomized and treated with any amount of study medication (COR-001 or placebo). Treatment classification will be based on the actual treatment received. This population will be used for the safety analyses.

11.3.3 *Analysis Windows and Baseline*

If data are collected by visit, the data will be analyzed by visit based on the protocol-planned visits. If multiple records are collected for a visit, the latest record will be used for the summary for that visit.

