- Description of changes in pre-dialysis, post-dialysis, and delta-serum Troponin and NT-proBNP (defined as the difference between the pre- and post-dialysis troponin) from baseline (mean of Screening) to Weeks 11 – 12
- Handgrip over time
- FACIT fatigue score over time

For the above efficacy variables, the observed values and changes from baseline will be summarized by treatment group using descriptive statistics using mITT and PP populations.

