Schedule of Events for the Safety Follow-Up and Extended Follow-Up Periods

Study Week	Safety Follow-Up Period					Extended F/U
	14	16	18	20	24/ET-2	35
Visit Window	± 3	± 3	± 3	± 3	± 3	± 7
Study Day	92	106	120	134	162	239
ESA and iron dosing per Appendix C						
Lab Panel 1 [CHEM]					X[a]	
Albumin	X		X			
Lab Panel 2 [LIP], Lp(a), serum pregnancy [1]					X[a]	
Lab Panel 3 [INFL1]	X[a]		X[a]		X[a]	
hsCRP	X[a]		X[a]		X[a]	X[a]
Pre-Albumin					X[a]	
Lab Panel 4 [SPRBC]	X[a]	X[a]	X[a]	X[a]	X[a]	
Lab Panel 5 [HEME]	X[a]	X[a]	X[a]	X[a]	X[a]	
Lab Panel 6 [IRON]	X[a]	X[a]	X[a]	X[a]	X[a]	
Lab Panel 7 [PK]	X[a]		X[a]			X[a]
Lab Panel 10 [ADA]					X[a]	X[a]
Lab Panel 11 [INFL2]	X[a]		X[a]		X[a]	X[a]
Local Lab INR [2]	X[a]	X[a]	X[a]	X[a]	X[a]	
12-lead ECG (pre-dialysis)			X		X	
Limited Physical Examination [3]			X		X	
Vital Signs (pre-dialysis) [4]	X	X	X	X	X	
Adverse Events	X					
Concomitant Medications	X					

[1] Serum pregnancy in women of childbearing potential only.

[2] Patients receiving warfarin only. May also be done using a point of care device.

[3] Limited physical exam to include skin, oropharynx, lungs, heart, abdomen, extremities (including feet), and any areas suggested by symptoms, with particular attention to signs of infection. May be performed by a physician-investigator or mid-level provider. Record abnormal findings in the source documents.

[4] Obtain blood pressure, heart rate, respiratory rate, and temperature: within 30 minutes prior to dialysis.

Every effort should be made to conduct the study visits on the same day of the week (e.g. on Wednesdays)

Laboratory test panels are defined in [Appendix D](#).

ET-2 = Early Termination Visit 2 (see [Section 5.8](#))

[a], [b], [c], [d] Please see [Footnote i](#)

Footnote i: Footnotes Common to All Schedule of Events' Tables

[a] Within 15 minutes prior to dialysis. Draw blood through either a peripheral needle stick or the arterial dialysis needle before connecting the arterial blood tubing or flushing the needle. Be sure that no saline or heparin is in the arterial needle or tubing prior to drawing the sample.

[b] Within 10 minutes after completing the infusion

If dialysis has ended, draw the sample after the machine has been turned off, either through a peripheral needle stick or from the arterial needle tubing prior to taking out the needle or arterial blood line/sample port.

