5.2 EXTENT OF EXPOSURE

Study drug will be administered by infusion once every other week for 11 weeks (6 doses) for the planned treatment regimens in the protocol. Exposure will be summarized using the cumulative frequency and percentage of subjects receiving ≥ 1 dose, ≥ 2 doses, ... ≥ 5 doses, and 6 doses by treatment group. Descriptive statistics (number of subjects, mean, standard deviation, minimum, median, quartiles range, and maximum) for exposure will be summarized. In addition, the exposure (in days), defined as the date of the last dose of study drug – date of the first dose of study drug + 1 will be summarized. Exposure with respect to COR-001-01 blood levels will be described in the Pharmacokinetics and Pharmacokinetic-Pharmacodynamic Modeling Data Analysis Plan.

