7.1 PRIMARY PHARMACODYNAMIC ANALYSIS

Endpoints:

The primary pharmacodynamic efficacy of COR-001 compared to placebo will be assessed by evaluating the following:

- Change from baseline (mean of Full Screening and Day 1 values) in hsCRP to Week 4 between treatment groups
 - The Day 29 value will be used for this analysis, reflecting at least 4 weeks of completed treatment. To ensure comparability to the post-baseline value, only the pre-dialysis Screening values will be used for the baseline.

Analysis Set:

Pharmacodynamic analysis population

Method:

Number of patients (n), mean, standard deviation (SD), median, quartiles (Q1 and Q3), minimum (min) and maximum (max) values for the observed value and change from baseline will be reported. The difference in changes (COR-001 - Placebo) will be presented. An analysis of covariance (ANCOVA) model will be used for this purpose with dose (specific active dose or placebo pooled) as a factor and baseline value as a covariate. The least square means for each dose, the least square mean differences from placebo along with the associated 95% confidence intervals (CIs) and p-values will be presented.

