10.2 INTERIM ANALYSIS

A single interim analysis will be conducted for the purpose of guiding future COR-001 clinical program activities. There are no stopping rules associated with the interim analysis and therefore no statistical adjustment for multiplicity will be made. The interim analysis will be conducted, at earliest, once all cohorts below that which exceed the MTD, excluding any expansion cohorts, have completed the study through Week 4 (or final visit, if prematurely discontinued).

The following endpoints will be assessed in the interim analysis:

- PD parameters: hsCRP, SAA, free and/or total serum IL-6, as well as, hemoglobin, TSAT, CHr, pre-albumin, and albumin
- Change in hemoglobin from screening to peak hemoglobin (defined as per subject absolute maximal hemoglobin in g/dL)
- Change from baseline (mean of Full Screening and Day 1 values) in Hemoglobin to Weeks 10-12, excluding hemoglobin values following a change in the total weekly ESA dose. A change is defined as the first time when the ESA weekly dose goes up by >25% or down by >25% relative to the previous week's dose.
- ERI
- Hemoglobin and ERI stratified by baseline ERI (<median or >=median)
- Cardiac biomarkers: Pro-NT-BNP and troponin
- MRI outcome: LVMI, LVESVI, LVEDVI, and LVEF
- Handgrip strength
- FACIT fatigue score

The summary approach for these listed endpoints will be the same as described in the SAP and will follow the specifications below for presentation in order to mask the treatment-level data:

- By masked treatment group (e.g. Treatment A, Treatment B, and etc.). Subjects receiving placebo from all cohorts will be combined as one of the treatment groups
 - Both PD analysis population and Per-Protocol analysis population will be performed on masked data
- Pooled treatment vs pooled placebo
- Pooled responder analysis defined as change from baseline in PD parameter for all patients (regardless of active vs placebo assignment) who achieve a $\geq 50\%$ reduction in hsCRP

To avoid identification of individual patients, the number of subjects, minimum, maximum values, and raw numbers for the percentages (i.e. numerator and denominator) will not be presented. Only the means, standard deviations, and percentages will be presented. The sponsor personnel will only receive the masked treatment group-level information and have no access to actual treatment-level information nor subject-level treatment information.

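### The PD population removes patients from the Week 4 endpoints because of doses due at or after the Week 4 sample, and no planned hsCRP or SAA analysis puts them back

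*SAP*

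**What the plan says.** **The exclusion.** SAP 2.2 excludes from the PD population patients with "≥ 2 Missed doses or ≥ 2 incorrect doses", plus other important deviations judged to affect PD interpretation and identified before unblinding. The dose rule has no time limit and is not tied to any endpoint. A patient who does not receive the assigned dose is classified by the highest dose received.

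**Where it is used.** SAP 7.1 (primary) and 7.2 (secondary) both name this population for their ANCOVAs, at Week 4 and at later times. For Week 4 hsCRP, SAP 7.1 states: "The Day 29 value will be used for this analysis, reflecting at least 4 weeks of completed treatment". In both documents ITT is the primary population only for disposition and baseline data.

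**The other sets.** Protocol 11.3.2 admits to the PD population ITT patients who received their assigned drug, "had any pharmacodynamic assessments, and did not have major protocol violations". It defines per-protocol as "The subset of the pharmacodynamics population that did not have a major protocol deviation", leaves the definition of such a deviation to the SAP, and makes this set the PD sensitivity analysis. The SAP never defines a per-protocol set. It mentions one only for the interim analysis (SAP 10.2): "Both PD analysis population and Per-Protocol analysis population will be performed on masked data". Protocol 11.4.4 says that the efficacy variables will be "summarized by treatment group using descriptive statistics using mITT and PP populations", and 11.4.1 also names mITT. That set appears in the abbreviation list but is not defined in 11.3.2.

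**The concern.** Whether a patient belongs in the Week 4 analysis should not depend on what happens after the Week 4 sample. Under SAP 2.2 it does: a patient with both early doses and a valid Day 29 hsCRP value leaves the Week 4 comparison if doses 4 and 5 are later missed.

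The later event may not be neutral. Protocol 8.1 withholds drug during a serious infection and 8.2 ends it after a severe reaction. If doses lost in these ways count as missed, tolerability decides who is analysed. It may do so differently on active drug and placebo, and infection bears directly on hsCRP. Protocol 4.3 and 8.2 keep patients who stop drug in follow-up, so usable PD data would be collected and then set aside.

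At stake is whether the PD differences and p-values can be read as randomised comparisons, and whether any planned analysis would show it if they cannot.

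**Working it through.** **Plan's own figure.** For hsCRP, the difference of 10.6 and SD of 17.3 give an effect size of 10.6/17.3 = 0.61. A two-sided t-test at 0.05 with 80% power needs 42.8, so 43 per group, as stated. The point below does not depend on this figure.

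**Step 1: doses before the Week 4 sample.**
- There are six doses, every other week (SAP 5.2), on Days 1, 15, 29, 43, 57 and 71 (Protocol Appendix A).
- The Day 29 hsCRP sample is drawn "Within 15 minutes prior to dialysis" (Appendix A, footnote a). Dose 3 is infused during that dialysis, so it comes after the sample.
- In the schedule, SAA is drawn on Day 22 and not on Day 29. This is also after two doses.
- Dose 1 defines Day 1 (Protocol synopsis), so a treated patient cannot have missed it.

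The most doses a treated patient can have missed by then is 2 − 1 = 1. The rule needs at least 2, so every missed-dose exclusion must count one of doses 3 to 6. This follows from the schedule alone. It does not extend to incorrect doses, because doses 1 and 2 could both be incorrect.

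**Step 2: if doses after discontinuation count as missed.** Stopping after dose 2, 3 or 4 leaves 4, 3 or 2 doses not given. Each case triggers exclusion from Week 4, although doses 1 and 2 may both have been received.

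**Step 3: how many patients.** The documents give no missed-dose rate. Assume an independent risk p of missing each of doses 2 to 6. Then P(excluded) = 1 − (1−p)^5 − 5p(1−p)^4. The share of those excluded who received dose 2 is (1−p) × P(at least 2 of doses 3–6 missed) / P(excluded).

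| p (assumed) | Excluded | Of 60 patients | Share with both doses before Week 4 |
|---|---|---|---|
| 2% | 0.4% | 0.2 | 60% |
| 5% | 2.3% | 1.4 | 59% |
| 10% | 8.1% | 4.9 | 58% |
| 15% | 16.5% | 9.9 | 56% |

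At 8:2 allocation, about 60 patients means 48 active and 12 placebo, so one placebo exclusion removes 1/12 = 8.3% of the control arm.

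**Step 4: power and bias.** For the stated hsCRP effect, a two-group t-test pooling all active doses has power of 46% at 48:12, 43% at 43:11 and 40% at 40:10. The loss of power is small. For bias, if a fraction f of one arm is excluded and differs from those kept by k SDs, that arm's mean shifts by f × k × 17.3. Both f and k are assumptions.
- f = 10%, k = 0.25 to 1: shift 0.43 to 1.73, or 4% to 16% of 10.6.
- f = 20%, k = 0.25 to 1: shift 0.87 to 3.46, or 8% to 33% of 10.6.

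**Step 5: could a planned analysis reveal it?**
- Per-protocol is by definition a subset of the PD population, so it cannot restore anyone.
- SAP 7.5 covers anaemia endpoints, ESA dose and ERI, not hsCRP or SAA. It splits the data or removes more.
- ITT is not assigned to any PD analysis, and mITT is undefined.

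**The case against.** The other side has several good arguments.

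- **The per-protocol set is not shown to be empty of purpose.** A reader might infer that the per-protocol and PD sets are identical, so that their difference is zero patients. The protocol wording overlaps almost completely if *violation* and *deviation* mean the same thing. But the protocol leaves the definition to the SAP, which gives none, and SAP 2.2 excludes only certain important deviations. A narrower per-protocol set is possible. This stands: the set is undefined, not proven identical. It remains a subset, however, so the excluded patients stay out.
- **Version lag.** The SAP was written on Amendment 2, and Amendment 3 added the per-protocol population to the protocol. SAP 12 allows later changes in a SAP amendment or the study report. This explains part of the gap but does not touch the open-ended dose rule.
- **Missed may not include withheld.** A reader might take missed doses to be consequences of treatment. Protocol 6.1.1 uses the word for a dose not given within 96 hours, with a missed dialysis visit as its example. For ESA and iron the protocol distinguishes missed from held doses. The link to tolerability is therefore one of two readings.
- **The number may be very small.** Staff give the infusions during routine dialysis, and a catch-up window applies. A loss of 10% to 20% of patients would need a risk of about 11% to 17% at each of doses 2 to 6, and no document supports such a rate.
- **Context.** The primary objective is safety, and an adherent set is defensible for an exposure-response question. SAP 2.2 tabulates exclusions by dose and treatment, so an imbalance in counts would be visible. Its effect on the estimate would not be.

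**Conclusion.** The point holds in this form: at Week 4, the missed-dose limb of SAP 2.2 selects entirely on information that is incomplete until at or after the measurement, and no planned hsCRP or SAA analysis restores the patients removed. This rests on the schedule and the definitions, not on any assumed rate.

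Two parts are conditional. Bias from tolerability needs withheld or post-discontinuation doses to count as missed, which the SAP leaves open. The size is unknown: 0.4% to 16.5% of patients follows only from an assumed independent risk of 2% to 15% per dose, and the shifts of 4% to 33% of the planned hsCRP difference rest on assumed exclusion rates and assumed differences between excluded and retained patients. The documents support neither an empty sensitivity analysis nor a known large loss of active patients.

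The change should be made before the PD results are analysed. It does not affect the primary safety objective, but the PD estimates and p-values come from this set. The dose rule is objective, which limits selection by analysts but not selection by treatment-related events.

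**What to change.** - Define mITT in the protocol and SAP as all randomised patients who received at least one dose and have a baseline and the endpoint value, analysed as randomised. Use it for the main PD ANCOVAs in SAP 7.1 and 7.2, in place of the highest-dose-received classification.
- Make the SAP 2.2 exclusions the defined per-protocol sensitivity set, and use that definition in SAP 10.2 and Protocol 11.3.2 and 11.4.4.
- State whether withheld doses and doses after permanent discontinuation count as missed for this set.
- For each endpoint, count only doses due before that endpoint's sample. For the Weeks 10–12 means, name the sample that closes the count.
- At Week 4 a two-missed-dose threshold limited in this way would exclude nobody. Define non-adherence there as any missed or incorrect dose among doses 1 and 2, so that the sensitivity set is not vacuous.

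The cost is wording in the SAP and protocol, and slight dilution of the PD effect from non-adherent patients in the main analysis. No new data are needed.
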